Release date: Edition number

MOD-3783

12 August 2016

GED version

### **Document history**

Document	Date of Issue	Summary of change

Release date: Edition number

GED version

[figure not shown]
12 August 2016

MOD-3783

Open Label Ib/IIa Trial of a Combination of IPH2201 and Ibrutinib in Patients with Relapsed, Refractory or Previously Untreated Chronic Lymphocytic Leukemia Protocol No. IPH-2201-202

### List of abbreviations

ADCC Antibody-dependent cell cytotoxicity

AE Adverse event

ALP Alkaline phosphatase

ALT (SGPT) Alanine amino transferase (serum glutamic pyruvic transaminase)

AML Acute Myeloid Leukemia

APTT Activated partial thromboplastin time

AR Adverse reaction

AST (SGOT) Aspartate amino transferase (serum glutamic oxalo-acetic transaminase)

ATM Ataxia-telengiectasia mutated

BCR B cell receptor
BM Bone Marrow
BP Blood pressure

BR Bendamustine plus rituximab
BTK Bruton's Tyrosine Kinase
CA Competent Authorities
CAR Chimeric antigen receptor
CD Cluster of Differentiation

GGT Gamma Glutamyl-Transferase
CHO Chinese Hamster Ovary cells

Cinf end Concentration at the end of the administration

CL Clearance CLB Chlorambucil

CLL Chronic Lymphocytic Leukemia
Cmax Maximum plasma concentration

CR Complete response

CRi CR with incomplete blood count recovery

CTL Cytotoxic T Lymphocytes

eCRF Electronic case report form

CRO Contract research organization

CRP C-reactive protein

CTCAE Common terminology criteria for adverse events (National Cancer Institute;

Version 4.03 to be used for this study)

DBP Diastolic Blood Pressure
DILI Drug-Induced Liver Injury
DLT Dose limiting toxicity

DSMB Data Safety Monitoring Board
DUN Dispensing Unique Number

EC Ethics committee
ECG Electrocardiogram

ECOG Eastern Cooperative Oncology Group performance status scale

EDC Electronic Data Capture
EFS Event-free survival

End of Study

### CONFIDENTIAL

Release date: Edition number 12 August 2016 MOD-3783

GED version

EOS End of treatment EOT Erythropoietin

EPO Fludarabine, cyclophosphamide and rituximab

FRC Fluorescence in situ FISH First Patient First Visit

FPFV Follow-Up

FU Good Clinical Practices

GCP Granulocyte colony stimulating factor

G-CSF Gamma Glutamyl Transferase

GGT Granular Mononuclear – Colony Stimulating Factor

GM-CSF Graft versus Leukemia

GvL Human Anti-Human antibody

HAHA Hepatitis B Virus

HBV Hepatitis B Surface Antigens

HBS Hematopoietic Cell Transplantation

HCT Hepatitis C Virus

HCV Human leukocyte antigen

HLA Human Immuno-deficiency virus

HIV High Group Level Term

HGLT High Level term

HLT Investigational medicinal product

IMP Intravenous(ly)

IV International Conference on Harmonization

ICH Interferon

IFN Immunoglobulin G

IgG Immunoglobulin Heavy Chain
IGHV Interleukin-2 (Aldesleukin)
IL-2 Investigational Medical Product

IMP Innate Pharma

IPH Institutional Review Board

IRB International Workshop on Chronic Lymphocytic Leukemia

IWCLL Inducible Tyrosine Kinase

ITK Interactive Web Response System IWRS Killer Immunoglobulin like Receptors

KIR Lactate Dehydrogenase
LDH Leukemia-free survival
LFS Lower Level Term
LLT Lymph Node

LN Leukemia-specific survival
LSS Last Patient Last Visit
LPLV Monoclonal antibody

mAb Monoclonal B Lymphocytosis

MBL Medical dictionary for regulatory activities
MedDRA Modification of Diet in Renal Disease

MDRD Myelodysplastic Syndrome

### CONFIDENTIAL

Release date: Edition number 12 August 2016 MOD-3783

GED version

MDS Major Histocompatibility Complex MHC Macrophage Inflammatory Protein-1β

MIP-1β Minimal Residual Disease
MRD Maximum tolerated dose
MTD Mean Corpuscular Volume

MCV National Cancer Institute (of the United States of America)

NCI Non-Hodgkin Lymphoma

NHL Natural Killer cells (immune system)

NK NOD-scid gamma
NSG Obinutuzumab
OBI Ofatumumab

OFA Overall Response Rate

ORR Overall Survival
OS Peripheral Blood

PB Peripheral Blood Mononuclear Cell

PBMC Pharmacodynamic
PD Principal investigator

PI Phosphatidyl inositol 3 kinase
PI3K Progression-free survival

PFS Pharmacokinetics

PK Per os

PO Time elapsed between P and R spike during ECG

PR Prothrombin time

PT Time for rapid depolarization of the right and left ventricles measured by ECG

QRS Time elapsed from beginning of the QRS complex to the end of the T wave

QT during ECG

QTc

Corrected "QT" interval Rheumatoid Arthritis

RA Receptor Saturation Assay

RSA Red blood cell(s)

RBC Serious adverse event

SAE Statistical Analysis Plan

SAP Systolic Blood Pressure

SBP Subcutaneous(ly)

SC Surveillance, Epidemiology and End Results

SEER Small Lymphocytic Lymphoma

SLL System Organ Class

SOC Suspected unexpected serious adverse reaction

SUSAR Spleen Tyrosine Kinase

SYK Time prior drug administration = Pre dose

H0 Terminal half-life T1/2 T Cell Receptor

TCR Tumor Lysis Syndrome
TLS Trial Material Manual
TMM Tumor Necrosis Factor

### CONFIDENTIAL

Release date: Edition number

GED version

TNF Time to Relapse
TTR Time to treatment
TTT UL16 Binding Proteins
ULBP Upper limit of normal

ULN White blood cell(s)
WBC Water For Injection

WFI

Release date: Edition number

GED version

### STUDY SYNOPSIS

[figure not shown]
Name of company: Innate Pharma	
Name of finished product: IPH2201	
Name of active substance: IPH2201 (formerly known as NNC01 NKG2A monoclonal antibody (CHO production), INN: monalizuma	
Study code: IPH2201-202	Development phase: lb/lla
Study title:	
Open label lb/lla trial of a combination of IPH2201 and ibrutir previously untreated chronic lymphocytic leukemia	nib in patients with relapsed, refractory or
Version:	Release Date: 12 August 2016
Principal coordinating investigator:	
Study centers:  Phase Ib: 4 sites (US sites)  Phase Ila: up to 10 sites (US sites)	
Study period (planned calendar):  FPFV: 9 November 2015  LPLV: 1Q 2019	
Rationale:	

CONFIDENTIAL

Release date: Edition number 12 August 2016

GED version MOD-3783

Release date: Edition number

MOD-3783

12 August 2016

GED version

### Study objectives:

### Phase Ib

- The primary objective of the phase Ib is to assess the safety of IPH2201 given IV as a single agent and in combination with ibrutinib in patients with relapsed, refractory or previously untreated chronic lymphocytic leukemia.
- The secondary objectives of the phase lb are:
  - 1) To determine the PK and PD of IPH2201 given concomitantly with ibrutinib, and to confirm the PK/PD relationship of IPH2201
    - ·
  - To document the anti-leukemic activity of the combination of IPH2201 and ibrutinib

### Phase IIa

- The primary objective of the phase IIa is to evaluate the anti-leukemic activity of the combination of IPH2201 and ibrutinib in patients with relapsed, refractory or previously untreated chronic lymphocytic leukemia.
- The secondary objectives are:
  - 1) To assess the safety of the combination of IPH2201 and ibrutinib
  - 2) To determine the PK and PD of IPH2201 given concomitantly with ibrutinib, and to confirm the PK/PD relationship of IPH2201

### Trial design:

Multicenter, open label Phase Ib/IIa study consisting of 2 parts:

- A part 1 dose escalation phase lb to confirm the safety of IPH2201 as a single agent during 4 weeks and thereafter combined with ibrutinib during 52 weeks
- · A part 2 single-arm phase IIa assessment of IPH2201 combined with ibrutinib during 52 weeks

During the phase lb, a 3+3 design will be employed. Four doses are planned to be assessed if MTD is not previously reached:

Dose level 1: 1 mg/kg Dose level 2: 2 mg/kg Dose level 3: 4 mg/kg

Dose level 4: 10 mg/kg

[figure not shown]
Three patients will be entered at each dose level. If a Dose Limiting Toxicity (DLT) is encountered in the initial cohort at a given dose level, that cohort will be expanded to a total of 6 patients.

Release date: Edition number 12 August 2016 MOD-3783

**GED** version

MTD will be considered to have been exceeded if >1/6 patients experience a DLT at that same dose level. MTD will be sought at the previous dose level by enrolling 3 additional patients, unless this cohort has been previously expanded to 6. If less than 2 out of 6 patients develop a DLT at that level, it will be defined as the MTD.

Dose-escalation will be based on a review by the safety committee of the data from all patients of the *current* cohort, after they have completed first 2 cycles of single agent IPH2201.

Introduction of ibrutinib at a new dose level will be allowed by the safety committee after review of the data of all patients of the *previous* cohort, after they have completed 2 cycles of IPH2201 in combination with ibrutinib.

During the phase IIa, patients will receive IPH2201 in combination with ibrutinib from the first day of the phase IIa.

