#### Trial design

The initial tested dose (1 mg/kg) is 10 times lower than the highest dose (10 mg/kg) tested and proven to be safe in the phase I trial of IPH2201.

During the dose escalation part of the study, IPH2201 will be given as a single drug for 2 cycles over a total of 28 days. Dose-escalation will be based on a review by the safety committee of the data from all patients of the *current* cohort, after they have completed 2 cycles of single agent IPH2201. Introduction of ibrutinib at a new dose level will be allowed by the safety committee after review of the data from all patients of the *previous* cohort, after they have completed 2 cycles of IPH2201 in combination with ibrutinib.

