# 3.5.2 Discontinuation of the study

The sponsor may discontinue the study at any time if an unacceptable toxicity is observed in a patient that leads the safety committee to recommend a transient or permanent discontinuation of the study. If the study is prematurely discontinued, all study data must be returned to Innate Pharma. In addition, the site must conduct final disposition of all unused study drug in accordance with Innate Pharma procedures for the study.

Release date: Edition number

GED version

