#### 9.3 SAFETY COMMITTEE

A safety committee will be constituted to monitor data and overall safety in this study in order to determine the dose to be administered to the patients after phase lb.

The safety committee will consist of:

- The principal investigators of the study
- A sponsor medical and pharmacologist representative
- The sub-investigators as optional members, including the Director of the division of Hematology at OSU as hematologist with high experience in CLL
- A methodologist or physicians with relevant expertise related to the reviewed safety issues can
  join the safety committee as optional member

The Safety Committee will review the data for progression and safety with data collected as following:

- During the dose escalation phase Ib of the trial, at each dose level after the completion of the 2 cycles of IPH2201 by the *last* patient of the cohort
- o During phase Ib, at each dose level the safety committee will also review patients data after completion of 2 cycles of IPH2201 in combination with ibrutinib by the *last* patient of the cohort
- o Furthermore, at any time during the phase lb, considering any additional safety information, the safety committee may decide to decrease the dose of IPH2201 to a lower dose level
- During the phase IIa of the trial, every six months
- The Safety Committee could also be involved at any time should a major safety issue occur.

The functions of the safety committee are multiple:

- To analyze the causality of the AEs in phase Ib
- At each dose level, to allow dose escalation as above described
- To select the dose of IPH2201 which will be assessed during the phase IIa, taking into account all the safety, pharmacology and anti-leukemia activity data gathered at each dose level, with a minimum of follow-up of 4 weeks after the introduction of ibrutinib, in the last patient enrolled in the dose escalation study. Such a dose may correspond to the MTD, to the highest tested dose level or to a lower dose level, chosen during or at the end of the dose escalation. The safety committee may therefore decide to stop prematurely the dose escalation, even if the MTD was not reached. The report of the safety committee will be forwarded to the FDA

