- To recommend the discontinuation of the study, transiently or permanently, or a decrease in the dose, after the occurrence of 2 unacceptable reactions in patients treated by the combination of IPH2201 and ibrutinib during the first or second phase of the study

DLTs and unacceptable reactions are defined as:

- Any grade 3 or grade 4 non hematologic toxicity
- o Grade 4 neutropenia (ANC < 500/μI) lasting ≥7 days after discontinuation of therapy in patients with pre-treatment ANC ≥ 1,000/μI
- o Grade 4 thrombocytopenia (platelet count <20,000/μl and/or ≥75% decrease from pre-treatment value)
- Grade 3 or 4 thrombocytopenia associated with bleeding
- Any dose delay due to AE for > 14 consecutive days

Such events will be considered as DLTs whenever they occurred during the first 4 cycles (8 weeks) of treatment in phase Ib (including 2 administrations of treatment with IPH2201 alone and 2 administrations of treatment with IPH2201 + ibrutinib).

Release date: Edition number

GED version

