3.2.1 Phase Ib

Monalizumab is administered as an intravenous infusion as a single agent during the first 2 administrations, at week 0 and week 2; ibrutinib is introduced as a combination therapy at week 4. Monalizumab is administered at week 4 and 6 and then every 4 weeks. Ibrutinib is administered orally once daily.

During the phase Ib, a 3+3 design will be employed. Four doses are planned to be assessed if MTD is not previously reached:

Dose level 1: 1 mg/kg

Dose level 2: 2 mg/kg

Dose level 3: 4 mg/kg

Dose level 4: 10 mg/kg

Three patients will be entered at each dose level. If a Dose Limiting Toxicity (DLT) is encountered in the initial cohort at a given dose level, that cohort will be expanded to a total of 6 patients. MTD will be considered to have been exceeded if >1/6 patients experience a DLT at that same dose level. MTD will be sought at the previous dose level by enrolling 3 additional patients, unless this cohort has been previously expanded to 6. If less than 2 out of 6 patients develop a DLT at that level, it will be defined as the MTD.

Dose-escalation will be based on a review by the safety committee of the data from all patients of the current cohort, after they have completed first 2 cycles of single agent monalizumab. Introduction of ibrutinib at a new dose level will be allowed by the safety committee after review of the data of all patients of the previous cohort, after they have completed 2 cycles of monalizumab in combination with ibrutinib.

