3.3 Sample Size Justification

3.3.1 Phase Ib

3 to 24 patients will be included.

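### The 3+3 rule has no written stop at 2 or 3 DLTs in the first three patients, and two DLT items end at grade 4, so an abrupt toxic death is not a DLT as written

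*Protocol*

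**What the plan says.** The Protocol synopsis (Trial design) and SAP section 3.2.1 describe the same 3+3 escalation over 1, 2, 4 and 10 mg/kg.

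- **Expansion.** The trigger is "If a Dose Limiting Toxicity (DLT) is encountered in the initial cohort at a given dose level"; in that case "that cohort will be expanded to a total of 6 patients".
- **Failure.** "MTD will be considered to have been exceeded if >1/6 patients experience a DLT at that same dose level". Further patients are then entered at the level below.
- **Size.** The Protocol synopsis plans 12 to 24 patients in phase Ib. SAP section 3.3.1 says "3 to 24 patients will be included".

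The DLT list appears in the synopsis (Safety Committee) and in Protocol section 9.3, and it also defines unacceptable reactions. It has five items:

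- non-hematologic toxicity of grade 3 or 4;
- grade 4 neutropenia lasting at least 7 days, subject to a baseline neutrophil count;
- grade 4 thrombocytopenia, by platelet count or percentage fall;
- thrombocytopenia of grade 3 or 4 with bleeding;
- a dose delay of more than 14 days because of an AE.

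Protocol Appendix IV treats grade 5 (fatal) as a grade of its own. SAP section 9.1 tabulates DLTs and does not redefine them.

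**The concern.** **Expansion rule.** No branch covers 2 or 3 DLTs in the first three patients. Two DLTs already exceed 1 in 6 whatever the next three patients show. If the expansion sentence is followed literally, those three are exposed to a failed dose without informing the MTD decision.

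**DLT list.** Two of its items are capped at grade 4. Other rules in the documents are open-ended: the re-dosing criteria (synopsis and Protocol section 3.3.3), the dose-suspension rule (Protocol section 3.3.1) and the AE tables (SAP section 9.3) all cover grade 3 and above. A toxic death with no earlier qualifying event would therefore enter the DLT count only by committee judgement. DLT occurrence and the MTD form a phase Ib primary endpoint. Because the same list defines unacceptable reactions, the gap also affects the committee's two-reaction trigger, which runs in both phases.

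**Working it through.** **Inputs from the documents.** Four dose levels, 3 to 6 patients each; expansion from 3 to 6 on a DLT; failure when more than 1 of 6 has a DLT. The planned size reproduces: 4 × 3 = 12 and 4 × 6 = 24.

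**Assumed input.** The documents give no true DLT rate p, so a range from 5% to 1/2 is shown. Protocol section 1.2.4.2 describes the single-agent 10 mg/kg dose as "tested and proven to be safe in the phase I trial of IPH2201", so the lower rates may be more relevant for the single-agent cycles.

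**Formulas.** Let X be the number of DLTs in the first three patients, Binomial(3, p), and X2 the number in the next three.

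- Expected patients at a level, literal text: 3 + 3·P(X ≥ 1).
- Expected patients if a cohort is expanded only at X = 1: 3 + 3·P(X = 1).
- Excess: 3·P(X ≥ 2).
- Expected extra DLTs: 3p·P(X ≥ 2).
- P(MTD exceeded), either rule: P(X ≥ 2) + P(X = 1)·P(X2 ≥ 1). It is the same under both because X ≥ 2 already guarantees at least 2 of 6.

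**Worked case, p = 1/3.** P(X = 0) = 8/27, P(X = 1) = 12/27, P(X ≥ 2) = 7/27 = 0.259.

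- Literal: 3 + 3 × 19/27 = 5.11 patients.
- With the stop: 3 + 3 × 12/27 = 4.33 patients.
- Excess: 3 × 7/27 = 0.78 patients.
- Extra DLTs: 0.78 × 1/3 = 0.26.
- P(MTD exceeded): 0.2593 + 0.4444 × 0.7037 = 0.572.

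| Assumed true DLT rate | P(2 or more of first 3) | Expected patients, literal | Expected patients, with stop | Excess patients | Extra DLTs | P(MTD exceeded), either rule |
|---|---|---|---|---|---|---|
| 5% | 0.007 | 3.43 | 3.41 | 0.02 | 0.001 | 0.027 |
| 10% | 0.028 | 3.81 | 3.73 | 0.08 | 0.008 | 0.094 |
| 1/6 | 0.074 | 4.26 | 4.04 | 0.22 | 0.037 | 0.220 |
| 1/4 | 0.156 | 4.73 | 4.27 | 0.47 | 0.117 | 0.400 |
| 1/3 | 0.259 | 5.11 | 4.33 | 0.78 | 0.259 | 0.572 |
| 1/2 | 0.500 | 5.63 | 4.13 | 1.50 | 0.750 | 0.828 |

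All figures are per dose level. The excess is an average: it is three patients when the case occurs and none otherwise. The further saving from stopping within the second three is not counted.

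**Grade 5, item by item.** No arithmetic applies, because the documents give no toxic-death rate.

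- The non-hematologic and bleeding items name grades 3 and 4 only.
- The neutropenia item needs a low count that persists for days. The other thrombocytopenia item needs a platelet count or percentage fall, which a dying patient may or may not have.
- A dose delay does not describe a death.
- A patient who first had a recorded grade 3 or 4 non-hematologic toxicity, or met a count criterion, already has a DLT.

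What remains outside the list is an abrupt toxic death with no earlier qualifying event. It is an SAE under Protocol section 9.1.1.2, and section 9.1.2.1 requires a new record when an event worsens, but neither provision makes it a DLT.

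**The case against.** **Expansion rule.** The text names a standard 3+3 design and speaks of one DLT in the singular. A second DLT meets the failure criterion at once, and the next sentence sends accrual to the level below. The SAP minimum of 3 patients fits a stop after one unexpanded cohort. Figures missing from the available copy might show the branches. This makes literal application unlikely, but the reading is not written in the visible text, and a minimum of 3 equally fits the committee ending escalation early.

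**Safeguards.** The committee reviews each level after the single-agent cycles and again after two combination cycles. At any time in phase Ib "the safety committee may decide to decrease the dose of IPH2201 to a lower dose level". The first patient at a level is treated at least 7 days before the others. Under Protocol section 3.5.2, "The sponsor may discontinue the study at any time if an unacceptable toxicity is observed in a patient". The committee can also recommend stopping or lowering the dose "after the occurrence of 2 unacceptable reactions in patients treated by the combination of IPH2201 and ibrutinib". These reduce the practical risk, but none is a mandatory stop at the second DLT. The committee and sponsor powers are discretionary, the 7-day gap concerns only the first patient at a level, and the last trigger omits the two single-agent administrations on which escalation is decided.

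**Size.** At 5% to 10% the average excess is at most 0.08 patients per level. The first failed level would usually end escalation, so the excess would usually arise once. Both points stand.

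**Grade 5.** Protocol section 9.1.1.5 says that when a patient dies of another disease, that disease is the event to report. This supports assessing the causal event against the DLT list. A fatal event is still grade 5, however, and the two items end at grade 4.

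**Timing.** The SAP carries a 2019 approval date and the first patient visit was in November 2015, so only protocol wording could govern accrual. That is correct.

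**Conclusion.** Both parts hold as wording faults of low severity. Applied as written, the expansion sentence treats three more patients after a level has failed. The average cost is 0.02 patients per level at an assumed 5% DLT rate, 0.22 at 1/6, 0.78 at 1/3 and 1.50 at 1/2, all of which rest on the assumed rate and on literal reading. The MTD pass/fail decision and the 24-patient maximum are unaffected. The DLT list leaves out an abrupt toxic death with no earlier qualifying event; that gap is narrow and cannot be quantified from the documents. A sensible committee would probably act correctly in both situations, but the plan leaves this to inference and discretion when a written rule would settle it.

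**What to change.** 1. In the Protocol synopsis, and in SAP section 3.2.1 for consistency, state that a cohort is expanded to 6 only if exactly 1 of the first 3 patients has a DLT, and that as soon as 2 patients at a level have had a DLT, accrual at that level stops and the MTD is declared exceeded.
2. In both DLT lists (synopsis and Protocol section 9.3), word the non-hematologic item and the thrombocytopenia-with-bleeding item as grade 3 or higher, including grade 5, except death due to CLL progression. The exception matches Protocol section 9.1.1.5.

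The cost is a wording change. Sample size and the pass/fail rule under expansion stay the same. The SAP edit only keeps the two documents aligned.

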### Follow-up period:

Treatment by IPH2201 will be limited to 56 weeks, or less, in the event that a complete response with undetectable MRD is documented for 2 months.

[figure not shown]
Treatment by ibrutinib will be at least administered until the end of the study follow-up period (up to 12 months after end of IPH2201 treatment), unless disease progression (International Workshop on Chronic Lymphocytic Leukemia (IWCLL)), untoward toxicity, or consent withdrawal leads to the premature interruption of the ibrutinib treatment.

Patients will be enrolled for a post study follow-up enabling the investigator to document disease progression (IWCLL) or death, for 3 additional years after the completion of their in study follow-up.

Release date: 12 August 2016
Edition number

GED version MOD-3783

